### 7.3.10.3. Pregnancy Testing

Urine pregnancy testing will be completed for all women at the time points specified in [Table 1](#). Pregnancy testing will be performed before administration of the first 5 mg aripiprazole test dose (where required) at Screening and before dosing on Day 1.

Results must be negative for initial study eligibility and continued participation.

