**Table 1: Schedule of Visits and Assessments**

	Screening	Treatment Period 						
		Day 1	Month 1	Month 2	Month 3 	Month 4	Month 5	Month 6 EOT/ET
		V1	V2	V3	V4	V5	V6	V7
Visit windows (days)		Day 1	22-36	37-64	65-92	93-120	121-148	149-183
4 week dosing target day		1	29	57	85	113	141	169
6 week dosing target day		1	May skip Visit 	43	85	May skip Visit 	127	169
Study Drug Administration		Injections are to be given monthly (6 total injections) or every 6 weeks (4 total injections) based on the dosing regimen selected; After Day 1, subsequent injections will occur 28 or 42 days following the previous injection						
Informed Consent	X							
Eligibility Criteria Review 	X	X						
Oral Aripiprazole Test Dose Administration 	X							
Drug Screen 	X							
12-Lead ECG	X							
Demographics and Medical History	X							
Reason for switching paliperidone/risperidone	X							
MINI (Modules I & J)	X							X
Height	X							
Pregnancy Testing 	X	X						

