 Urine pregnancy testing will be completed for ALL women. At screening, pregnancy test should be completed prior to the administration of the first oral aripiprazole test dose, where applicable. On Day 1, testing will be performed before dosing.

 Full physical examination at screening; brief physical examination on Day 1; symptom directed physical exams may be performed as needed at the Investigator's discretion.

 Vital signs include blood pressure, heart rate, respiratory rate, and body temperature,

 Includes biochemistry (including prolactin), hematology, and urinalysis.

 Prolactin only will be measured at Month 1, Month 2 and Month 3.

Modified MSQ question #1 only at screening; the entire modified MSQ will be completed at Visit 8 (EOT)

The injection site and surrounding area will be evaluated following each injection and monitored so long as there are reactions to be monitored; if there are no observed reactions, continuing evaluation is not necessary

“Baseline” version used at screening; “since last visit” used at all subsequent visits

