#### **7.4.2. Contraception and Pregnancy**

All male and female subjects must agree to use an acceptable method of contraception for the duration of the study unless they are surgically sterile or post-menopausal (see below). The following are considered acceptable methods of contraception:

1. Double-barrier protection (eg, a condom with spermicide or a diaphragm with spermicide)
2. Intrauterine device (IUD)
3. Oral contraceptive pills or other hormonal methods (eg, a vaginal ring, contraceptive patch, contraceptive implant)

Subjects who are abstinent are eligible, provided they agree to use an acceptable contraceptive method should they become sexually active.

Subjects who are surgically sterile are exempt from the requirement to use contraception. Women who have undergone a hysterectomy, bilateral tubal ligation, or bilateral salpingo-oophorectomy are considered surgically sterile. Men who have undergone a vasectomy or bilateral orchectomy are considered surgically sterile. Partner vasectomy is not considered an approved acceptable method of contraception for a female subject.

Women who are postmenopausal are also exempt from the requirement to use contraception. For the purpose of this study, postmenopausal is defined as the permanent cessation of menstruation for at least 12 months prior to screening in women who are 45 years of age or older.

If a subject becomes pregnant while participating in the study, she will be discontinued from study drug immediately. Pregnancy is not considered an AE, however pregnancy, whether a female study subject or the partner of a male study subject, must be immediately documented on a Pregnancy Form and faxed to **PPD** at the SAE reporting fax number ([Section 13.5](#)) within 24 hours of the investigator becoming aware of the pregnancy. Additional follow-up may be required.

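### Section 7.3.10.3 makes continued participation depend on a negative pregnancy test, but the protocol schedules no test after the first injection

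*Protocol*

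**What the plan says.** All the relevant text is in the protocol; the SAP does not deal with pregnancy testing.

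- **The condition (Section 7.3.10.3).** "Results must be negative for initial study eligibility and continued participation".
- **When tests are done (same section).** "Urine pregnancy testing will be completed for all women at the time points specified in" Table 1. The section then names the occasions: "Pregnancy testing will be performed before administration of the first 5 mg aripiprazole test dose (where required) at Screening and before dosing on Day 1".
- **Schedule (Table 1).** The pregnancy-testing row is marked at Screening and Day 1. It has no mark at V2 to V6 or at the Month 6 end-of-treatment/early-termination visit (V7). Footnote 7 names the same two occasions, for all women; on the second it says "On Day 1, testing will be performed before dosing".
- **Consequence of pregnancy (Section 7.4.2).** "If a subject becomes pregnant while participating in the study, she will be discontinued from study drug immediately". The pregnancy must be reported within 24 hours of the investigator learning of it. Section 13.1 repeats the withdrawal from study drug, and Section 6.3 lists pregnancy among the reasons for discontinuation.
- **Other protections.** Contraception is required throughout the study, with exemptions for surgically sterile and postmenopausal subjects (Section 6.1, criterion 9; Section 7.4.2). Women who plan a pregnancy during the study are excluded (Section 6.2, criterion 1).

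**The concern.** Section 7.3.10.3 sets two conditions, and both depend on a test result: one for entering the study and one for staying in it. The schedule produces results that can serve the first. After the first injection it produces none, so a site that follows Table 1 exactly has nothing with which to check the second.

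This matters because dosing continues. Section 8.1 describes the product as releasing slowly over a prolonged period, so an injection given before a pregnancy is recognised cannot be taken back. The discontinuation rule in Section 7.4.2 and its 24-hour reporting clock both start from knowledge of the pregnancy, and no section says how that knowledge would arise after Day 1. Self-report is also a weaker signal than usual here: the modified UKU scale (Appendix E, item 4.8) rates reduced or absent menstruation as a possible side effect, so a missed period could be put down to treatment.

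**Working it through.** **Inputs, all from Protocol Table 1**

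- Totals: "Injections are to be given monthly (6 total injections) or every 6 weeks (4 total injections) based on the dosing regimen selected".
- Spacing: "After Day 1, subsequent injections will occur 28 or 42 days following the previous injection".
- End-of-treatment target: Day 169.
- Last scheduled pregnancy test: Day 1, before dosing.

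**Step 1. Reproduce the plan's injection totals.** Injection day = 1 + interval × k, for k = 0, 1, 2, …, stopping before Day 169.

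- Interval 28: Days 1, 29, 57, 85, 113, 141. That is 6 injections, as stated. (1 + 28 × 6 = 169, the final visit.)
- Interval 42: Days 1, 43, 85, 127. That is 4 injections, as stated. (1 + 42 × 4 = 169.)

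**Step 2. Count injections after the last scheduled test.**

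| Regimen | Total | After Day 1 | Days since the Day 1 test |
|---|---|---|---|
| Monthly | 6 | 6 − 1 = 5 | 28, 56, 84, 112, 140 |
| Every 6 weeks | 4 | 4 − 1 = 3 | 42, 84, 126 |

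Section 8.1 allows a change of schedule after the second injection. With the 4 to 6 doses given in Section 7.1, the planned count for a completer is 3 to 5.

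**Step 3. Length of the untested period.** 169 − 1 = 168 days on target days. The V7 window is Days 149 to 183, so the range is 149 − 1 = 148 to 183 − 1 = 182 days.

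**Step 4. Look for any other source of a result.**

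- Section 7.3.10.2 lets the investigator repeat laboratory assessments, but it concerns the tests in Table 2, and Table 2 has no pregnancy test.
- Section 7.1 allows additional outpatient assessments and Section 7.3.6 allows symptom-directed examinations. Neither mentions pregnancy testing.
- V7, which also serves as the early-termination visit, has no test.

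**Step 5. Rule out a reading fault.** The table row, its footnote and the section text all give the same two occasions, so the absence of later tests does not come from a badly extracted table.

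**The case against.** The best defence is that the sentence refers only to the two tests named just before it. Participation begins at consent, and oral test doses may be given during screening. A negative Screening result could then serve eligibility, and a negative Day 1 result could serve continuation to the first injection, with nothing missing. This reading is possible, but the protocol does not state it. It is also strained, because Day 1 is itself an eligibility review (Section 7.1; Table 1). If it is what the sponsor meant, the sentence should say so.

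Three further points stand in part.

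- The discontinuation rule in Section 7.4.2 applies however a pregnancy comes to light and needs no scheduled test.
- Contraception and exclusion criterion 1 reduce the chance of a pregnancy. They are an agreement and an intention, however, and Section 7.3.10.3 asks for results.
- Investigators may add assessments. Discretion helps detection, but it does not meet a condition worded as mandatory.

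A reader might infer something stronger: that the pregnancy safeguard cannot work at all after Day 1, or that pregnancies would go unnoticed. The documents do not support that. Only scheduled testing is absent; contraception, self-report, unscheduled assessment and the discontinuation rule remain. The figure of five injections is the monthly maximum per woman and does not estimate exposed pregnancies.

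**Conclusion.** The inconsistency is real and should be resolved. On the ordinary meaning of Section 7.3.10.3, continued participation rests on a negative result that the schedule does not generate after Day 1. The uncovered part of treatment is 5 of 6 injections on monthly dosing or 3 of 4 on six-weekly dosing, over 168 days on target dates.

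This rests on two assumptions: that continued participation extends beyond the first injection, and that sites do only the tests in Table 1. If the narrower reading is intended, the defect is one of wording.

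The practical consequence cannot be sized. The trial plans about 50 subjects of both sexes aged 18 to 65, and the documents give neither the number of women of childbearing potential nor a pregnancy rate. Sample size, endpoints and planned analyses are unaffected.

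**What to change.** Reconcile the Table 1 pregnancy-testing row, footnote 7, Section 7.3.10.3 and Section 7.4.2, in one of two ways:

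1. Amend the row and footnote 7 so that testing at existing visits supports the continued-participation condition; or
2. State in Section 7.3.10.3 that the condition refers only to the Screening and Day 1 results, so that it no longer implies later testing.

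The choice between them is the sponsor's, as are the timing of any added tests, which women are tested (footnote 7 now covers all women) and how a positive result is handled.

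Either way the cost is a protocol amendment with the IRB re-approval that Section 17.1 requires. The second option is a wording change only. The first adds a few urine tests at visits already held. Six visits follow Day 1 (V2 to V7), so six per woman is the ceiling for scheduled visits.

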### 7.3.11. Drug Dispensation and Reconciliation

[Section 8](#) provides information related to drug dispensing procedures. Study drug will be administered at the time point(s) specified in [Table 1](#) and reviewed with the subject.

### 7.3.12. Adverse Event Monitoring

AEs will be monitored continuously from the time a subject signs the informed consent document until the completion of the final study visit (see [Table 1](#)). AEs and serious adverse

events (SAEs) are defined in [Section 13.1](#) and [13.2](#), respectively. [Section 13.4](#) provides guidance on the monitoring and reporting requirements for AEs. [Section 13.5](#) provides guidance on the reporting requirements for SAEs.

### **7.3.13. Efficacy Assessments**

#### **7.3.13.1. Clinical Global Impressions-Severity**

The investigator or designee will complete the Clinical Global Impression – Severity (CGI-S) ([Appendix C](#)) scale ([Guy 2000](#)) at screening and at every time point as identified in [Table 1](#).

#### **7.3.13.2. Brief Psychiatric Rating Scale**

The investigator or designee will complete the Brief Psychiatric Rating Scale (BPRS) ([Appendix D](#)) at screening and at every time point as identified in [Table 1](#).

### **7.3.14. Quality of Life, Daily, and Social Functioning Assessments**

#### **7.3.14.1. Sexual Functioning Subscale from Udvalg for Kliniske Undersøgelser Side Effect Rating Scale**

The sexual functioning subscale from the UKU Side Effect Rating Scale ([Appendix E](#)) contains 7 items for males and 9 items for females ([Lingjaerde, Ahlfors et al. 1987](#), [Lindstrom, Lewander et al. 2001](#)). Each item is rated on a 4-point scale (0 = none or doubtful, 1 = present to a mild degree, 2 = present to a moderate degree, and 3 = present to a severe degree). This scale will be completed by the patient at the time points specified in [Table 1](#).

#### **7.3.14.2. Changes in Sexual Functioning Questionnaire Short Form**

The CSFQ-14 ([Appendix F](#)) is a 14-item rating scale that evaluates sexual functioning in each domain of the sexual response cycle ([Keller, McGarvey et al. 2006](#)). The subjects rate their sexual functioning on a 5-point Likert scale. Higher scores indicate more sexual dysfunction. The CSFQ will be completed by the patient at the time points specified in [Table 1](#).

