## CHANGES IN SEXUAL FUNCTIONING QUESTIONNAIRE (CSFQ-F-C)

Patient Name \_\_\_\_\_

**NOTE: This is a questionnaire about sexual activity and sexual function. By sexual activity, we mean sexual intercourse, masturbation, sexual fantasies and other activity.**

1. Compared with the most enjoyable it has ever been, how enjoyable or pleasurable is your sexual life right now?

- 1-No enjoyment or pleasure
- 2-Little enjoyment or pleasure
- 3-Some enjoyment or pleasure
- 4-Much enjoyment or pleasure
- 5-Great enjoyment or pleasure

2. How frequently do you engage in sexual activity (sexual intercourse, masturbation, etc.) now?

- 1-Never
- 2-Rarely (once a month or less)
- 3-Sometimes (more than once a month, up to twice a week)
- 4-Often (more than twice a week)
- 5-Every day

3. How often do you desire to engage in sexual activity?

- 1-Never
- 2-Rarely (once a month or less)
- 3-Sometimes (more than once a month, up to twice a week)
- 4-Often (more than twice a week)
- 5-Every day

4. How frequently do you engage in sexual thoughts (thinking about sex, sexual fantasies) now?

- 1-Never
- 2-Rarely (once a month or less)
- 3-Sometimes (more than once a month, up to twice a week)
- 4-Often (more than twice a week)
- 5-Every day

5. Do you enjoy books, movies, music or artwork with sexual content?

- 1-Never
- 2-Rarely (once a month or less)
- 3-Sometimes (more than once a month, up to twice a week)
- 4-Often (more than twice a week)
- 5-Every day

6. How much pleasure or enjoyment do you get from thinking about and fantasizing about sex?

- 1-No enjoyment or pleasure
- 2-Little enjoyment or pleasure
- 3-Some enjoyment or pleasure
- 4-Much enjoyment or pleasure
- 5-Great enjoyment or pleasure

7. How often do you become sexually aroused?

- 1-Never
- 2-Rarely (once a month or less)
- 3-Sometimes (more than once a month, up to twice a week)
- 4-Often (more than twice a week)
- 5-Every day

Today's Date \_\_\_\_\_

8. Are you easily aroused?

- 1-Never
- 2-Rarely (much less than half the time)
- 3-Sometimes (about half the time)
- 4-Often (much more than half the time)
- 5-Always

9. Do you have adequate vaginal lubrication during sexual activity?

- 1-Never
- 2-Rarely (much less than half the time)
- 3-Sometimes (about half the time)
- 4-Often (much more than half the time)
- 5-Always

10. How often do you become aroused and then lose interest?

- 1-Never
- 2-Rarely (much less than half the time)
- 3-Sometimes (about half the time)

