- 4-Often (much more than half the time)
- 5-Always

11. How often do you experience an orgasm?

- 1-Never
- 2-Rarely (much less than half the time)
- 3-Sometimes (about half the time)
- 4-Often (much more than half the time)
- 5-Always

12. Are you able to have an orgasm when you want to?

- 1-Never
- 2-Rarely (much less than half the time)
- 3-Sometimes (about half the time)
- 4-Often (much more than half the time)
- 5-Always

13. How much pleasure or enjoyment do you get from your orgasms?

- 1-No enjoyment or pleasure
- 2-Little enjoyment or pleasure
- 3-Some enjoyment or pleasure
- 4-Much enjoyment or pleasure
- 5-Great enjoyment or pleasure

14. How often do you have painful orgasm?

- 1-Never
- 2-Rarely (once a month or less)
- 3-Sometimes (more than once a month, up to twice a week)
- 4-Often (more than twice a week)
- 5-Every day

\_\_\_\_\_ = Pleasure (Item 1)

\_\_\_\_\_ = Desire/Frequency (Item 2 + Item 3)

\_\_\_\_\_ = Desire/Interest (Item 4 + Item 5 + Item 6)

\_\_\_\_\_ = Arousal/Excitement (Item 7 + Item 8 + Item 9)

\_\_\_\_\_ = Orgasm/Completion (Item 11 + Item 12 + Item 13)

\_\_\_\_\_ = Total CSFQ Score (Items 1 to 14)

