## CHANGES IN SEXUAL FUNCTIONING QUESTIONNAIRE (CSFQ-M-C)

Patient Name \_\_\_\_\_

Today's Date \_\_\_\_\_

**NOTE:** This is a questionnaire about sexual activity and sexual function. By sexual activity, we mean sexual intercourse, masturbation, sexual fantasies and other activity.

1. Compared with the most enjoyable it has ever been, how enjoyable or pleasurable is your sexual life right now?

- 1-No enjoyment or pleasure
- 2-Little enjoyment or pleasure
- 3-Some enjoyment or pleasure
- 4-Much enjoyment or pleasure
- 5-Great enjoyment or pleasure

2. How frequently do you engage in sexual activity (sexual intercourse, masturbation, etc.) now?

- 1-Never
- 2-Rarely (once a month or less)
- 3-Sometimes (more than once a month, up to twice a week)
- 4-Often (more than twice a week)
- 5-Every day

3. How often do you desire to engage in sexual activity?

- 1-Never
- 2-Rarely (once a month or less)
- 3-Sometimes (more than once a month, up to twice a week)
- 4-Often (more than twice a week)
- 5-Every day

4. How frequently do you engage in sexual thoughts (thinking about sex, sexual fantasies) now?

- 1-Never
- 2-Rarely (once a month or less)
- 3-Sometimes (more than once a month, up to twice a week)
- 4-Often (more than twice a week)
- 5-Every day

5. Do you enjoy books, movies, music or artwork with sexual content?

- 1-Never
- 2-Rarely (once a month or less)
- 3-Sometimes (more than once a month, up to twice a week)
- 4-Often (more than twice a week)
- 5-Every day

6. How much pleasure or enjoyment do you get from thinking about and fantasizing about sex?

- 1-No enjoyment or pleasure
- 2-Little enjoyment or pleasure
- 3-Some enjoyment or pleasure
- 4-Much enjoyment or pleasure
- 5-Great enjoyment or pleasure

7. How often do you have an erection related or unrelated to sexual activity?

- 1-Never
- 2-Rarely (once a month or less)
- 3-Sometimes (more than once a month, up to twice a week)
- 4-Often (more than twice a week)
- 5-Every day

8. Do you get an erection easily?

- 1-Never
- 2-Rarely (much less than half the time)
- 3-Sometimes (about half the time)
- 4-Often (much more than half the time)
- 5-Always

9. Are you able to maintain an erection?

- 1-Never
- 2-Rarely (much less than half the time)
- 3-Sometimes (about half the time)
- 4-Often (much more than half the time)
- 5-Always

10. How often do you experience painful, prolonged erections?

- 5-Never
- 4-Rarely (once a month or less)
- 3-Sometimes (more than once a month, up to twice a week)

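### The protocol states the CSFQ-14 direction opposite to its own forms, and those forms score the identical item 14 in opposite directions for women and men

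*Protocol*

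**What the plan says.** Protocol 7.3.14.2 describes the CSFQ-14 as a 14-item self-rating on a 5-point scale, points to Appendix F for the form, and states: "Higher scores indicate more sexual dysfunction". Neither document says anything else about the direction of this scale.

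Appendix F prints one form per sex.

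- On both forms, items 1 to 9 and 11 to 13 run from 1 (no enjoyment, or never) to 5 (great enjoyment, always, or every day). Item 1, for example, ends at "5-Great enjoyment or pleasure".
- Female item 10, "10. How often do you become aroused and then lose interest", is coded from 1 for never to 5 for always. Female item 14, "14. How often do you have painful orgasm", is coded from 1 for never to 5 for every day, so one of its answers reads "2-Rarely (once a month or less".
- Male item 10, "10. How often do you experience painful, prolonged erections", is a different question and is coded from 5 for never down to 1. Male item 14 has the same wording as female item 14 but is also coded from 5 for never down to 1.
- Both forms define five subscales and then "Total CSFQ Score (Items 1 to 14", with no recoding note.

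SAP 3.7.10 summarizes observed values and changes for each subscale and the total, by gender and overall. It gives no direction and no recode. SAP sections 6 and 7 leave dataset and programming specifications to separate documents.

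**The concern.** There are two faults of different kinds.

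The first is interpretation. Anyone who reads the tables by the plan's only direction statement would take an improvement in sexual function for a deterioration, in every subscale and in the total. No computed value changes, but in a single-arm descriptive analysis the sign of the mean change is most of what a reader takes away.

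The second is derivation. If the female form was captured and summed as printed, the female total adds two items that run against the other 12, and the overall total pools two different scorings.

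**Working it through.** The plan gives no figure to reproduce. The inputs are the printed codes in Appendix F.

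**Direction by item.** Male form: 14 of 14 items have higher as better, because both problem items (10 and 14) are reversed. Female form: 12 of 14 have higher as better; items 10 and 14 have higher as worse.

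**Item 14, same answer on each form.**

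| Answer | Female code | Male code | Female minus male |
|---|---|---|---|
| Never | 1 | 5 | -4 |
| Rarely | 2 | 4 | -2 |
| Sometimes | 3 | 3 | 0 |
| Often | 4 | 2 | +2 |
| Every day | 5 | 1 | +4 |

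Item 10 asks different things by sex, so item 14 is the only like-for-like contradiction.

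**What the subscales use.** Items per subscale: 1 + 2 + 3 + 3 + 3 = 12, namely items 1 to 9 and 11 to 13. All are higher-is-better on both forms, so every subscale contradicts 7.3.14.2. The total minus the subscales equals item 10 + item 14. From worst to best function this runs 5 + 5 = 10 down to 1 + 1 = 2 for women as printed, and 2 up to 10 for men.

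**Range of the total.**

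- Female as printed: worst 12×1 + 5 + 5 = 22; best 12×5 + 1 + 1 = 62.
- Female with items 10 and 14 recoded: worst 14×1 = 14; best 14×5 = 70, which matches the male form.
- Female with item 14 alone recoded: 18 to 66, which still does not match. Both items would need recoding.

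**Change from baseline in a woman.** Let F be the net change on the other 12 items and d > 0 the steps of improvement on items 10 and 14 combined. The total changes by F - d as printed and by F + d if recoded, an error of 2d. The signs are opposite only when -d < F < d.

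| F | d | As printed | Recoded | Sign reversed |
|---|---|---|---|---|
| 1 | 2 | -1 | +3 | yes |
| -3 | 2 | -5 | -1 | no |
| 3 | 2 | +1 | +5 | no |

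If the two items do not move, the error in change is zero.

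**Group means.** The documents give neither a response distribution nor the share of women, so both of the following are assumptions. For a mean d among women of 0 to 1 step, the error in the women's mean change is 2 × mean d = 0 to 2.0 points. With a share p of women, the error in the overall mean change is 2 × p × mean d: 0 to 0.4 points at p = 0.20, and 0 to 1.0 point at p = 0.50.

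**The case against.** The strongest reply is that the coding fault is shown only on a form listed as a sample. The dataset and programming specifications are separate documents and may already contain a recode. That stands: the mismatch on the printed forms is certain, but an error in the analysis is only a possible consequence. It does not rescue 7.3.14.2, because recoding items 10 and 14 would leave the other 12 items opposite to the sentence.

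A second reply is that neither form labels its direction, and that for pure frequency items, such as how often one has sexual thoughts, calling more frequent better is an inference. The trial's own UKU form asks about increased desire as a side effect. This is fair as a caution on the item counts and the worst-to-best ranges. The enjoyment and ability items are unambiguous, however, and the male form reverses exactly its two problem items, which makes sense only if high codes are meant to be good.

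Third, the SAP is silent on direction for other scales too. That is true, but for the CSFQ-14 the silence leaves a wrong protocol sentence as the only guide.

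Finally, the reach is small. The outcome falls under a secondary objective and is descriptive, with no test or threshold. Table 1 schedules one post-baseline assessment (Month 6 or early termination). The coding issue leaves men's results and all subscales untouched. All of this stands and limits the weight of the point. The sizes given for group means are assumed ranges that start at zero.

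**Conclusion.** The concern holds. The direction sentence in 7.3.14.2 contradicts the forms it cites, and the contradiction covers all five subscales and the total. The identical item 14 is printed with opposite codes by sex, female item 10 is also unreversed, and nothing in the supplied documents resolves either. Unless a recode exists elsewhere, the female total has a range of 22 to 62 instead of 14 to 70, each woman's change is off by 2d, and the pooled total mixes two scorings. The effect on this trial's means cannot be known from the documents. The point should be fixed because a stated rule is wrong as written; its reach is limited to the reading of one descriptive secondary scale and, for the coding, to the female and pooled totals.

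**What to change.** First check the fielded form (and the Appendix F PDF), the instrument's scoring instructions and the dataset specification. Then:

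- If they match Appendix F as printed, correct 7.3.14.2 to say that higher scores indicate better sexual functioning, and state in SAP 3.7.10 that an increase is improvement.
- If female items 10 and 14 were captured as printed and the scoring instructions call for one direction, state in SAP 3.7.10 that each is recoded as 6 minus the recorded value before the total is formed.
- If a recode already exists, cite it in SAP 3.7.10 instead.

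The cost is one check, one corrected protocol sentence, one or two SAP sentences and at most one derivation line. No new data are needed.
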